- 691 • Participants who do not wish to continue in the study will transition back to personal insulin
692 pump, or to resumption of MDI. The 13-Week visit will serve as the final study visit for
693 these participants.
- 694 • Participants who agree to continue in the study will be provided with sufficient study
695 supplies to last until the 26-Week visit
- 696 • Participants who had been randomized to PLGS for the preceding 13-week period will be
697 given a CLC pump and will receive refresher training on the CLC system at the
698 discretion of the investigator, using a subset of the topics described in section 3.2.1
699 above.

700 **3.8.4 26-Week Visit and Subsequent Visits Every 13 Weeks**

701 Until the point that the CLC system is commercially available (but not longer than 15 months
702 after study enrollment), participants will return to the clinic for a visit every 13 weeks (± 7 days),
703 beginning with a 26-Week visit (± 7 days), during which the following will occur:

- 704 • HbA1c determination using the DCA Vantage or similar point of care device
- 705 • Completion of questionnaire (26-Week visit only)
- 706 • Urine pregnancy test for all women of child-bearing potential
- 707 • Weight measurement
- 708 • Assessment of adverse events, adverse device effects, and device issues
- 709 • Download of device data (study system or personal pump and study CGM, study BG meter,
710 study ketone meter)

711 **3.8.5 Final Visit**

712 When the CLC system becomes commercially available from the manufacturer (or 15 months
713 has elapsed since enrollment), participants will return to the clinic within a 6-week period for a
714 final study visit. The 6-week transition period is intended to provide an opportunity for the
715 participant to complete the logistics of obtaining the system commercially (insurance, etc.). The
716 following will occur during the final visit:

- 717 • HbA1c determination using the DCA Vantage or similar point of care device (skipped if the
718 prior 13-Week clinic visit occurred in the preceding 2-week period)
- 719 • Completion of questionnaires
- 720 • Weight measurement (skipped if the prior 13-Week clinic visit occurred in the preceding 2-
721 week period)
- 722 • Assessment of adverse events, adverse device effects, and device issues

- 723 • Download of device data (study system or personal pump and study CGM, study BG meter,
724 study ketone meter)

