1434 1 comparing 3 months of PLGS baseline to 3 months of CLC follow up using paired t-tests
1435 unless the data are highly skewed in which case a transformation or a robust statistical method
1436 will be used instead.

1437 Safety outcomes will be tabulated. Device issues, protocol adherence, and the other variables
1438 listed above for tabulation will be described or summarized as indicated.

1439

1440 **Chapter 9: Data Collection and Monitoring**

1441 **9.1 Case Report Forms and Device Data**

1442 The main study data are collected through a combination of electronic case report forms
1443 (CRFs) and electronic device data files obtained from the study software and individual
1444 hardware components. These electronic device files and electronic CRFs from the study
1445 website are considered the primary source documentation.

1446 When data are directly collected in electronic case report forms, this will be considered the
1447 source data. Each participating site will maintain appropriate medical and research records for
1448 this trial, in compliance with ICH E6 and regulatory and institutional requirements for the
1449 protection of confidentiality of participants.

1450 **9.2 Study Records Retention**

1451 Study documents should be retained for a minimum of 2 years after the last approval of a
1452 marketing application in an ICH region and until there are no pending or contemplated marketing
1453 applications in an ICH region or until at least 2 years have elapsed since the formal
1454 discontinuation of clinical development of the investigational product. These documents should
1455 be retained for a longer period, however, if required by local regulations. No records will be
1456 destroyed without the written consent of the sponsor, if applicable. It is the responsibility of the
1457 sponsor to inform the investigator when these documents no longer need to be retained.

1458 **9.3 Quality Assurance and Monitoring**

1459 Designated personnel from the Coordinating Center will be responsible for maintaining quality
1460 assurance (QA) and quality control (QC) systems to ensure that the clinical portion of the trial is
1461 conducted and data are generated, documented and reported in compliance with the protocol,
1462 Good Clinical Practice (GCP) and the applicable regulatory requirements. Adverse events will
1463 be prioritized for monitoring.

1464 A risk-based monitoring (RBM) plan will be developed and revised as needed during the course

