106 • Baseline: CGM data from the last 13 weeks of the preceding 6-month RCT (i.e. 90 days prior to
107 the final visit of the preceding RCT) will be used to calculate baseline metrics. At least 168 hours
108 of CGM data will be required for the calculation. Baseline CGM metrics will be treated as
109 missing for any participants who have fewer than 168 hours of data in the last 13 weeks of the
110 preceding RCT.
111 • Follow-up: CGM metrics will be calculated by pooling all data starting with randomization day
112 in the current study (or enrollment day, for subjects not randomized) and up through previous
113 midnight of the earlier of day 98 from enrollment/randomization or the 13-week visit date, will
114 be included. At least 168 hours of CGM data will be required for the calculation.
115 • All CGM metrics at baseline and during follow-up will be calculated giving equal weight to each
116 sensor reading for each participant.
117 • Daytime and nighttime
118 ○ CGM metrics above will also be calculated for daytime period (06:00AM to 11:59PM)
119 and overnight period (00:00AM to 05:59AM) separately.
120 ○ Minimum 126 hours of CGM data will be required to calculate daytime metrics and
121 minimum 42 hours of CGM data will be required to calculate overnight metrics.
122 ○ If <168 hours of CGM data available for combined day and night, then CGM metrics will
123 not be calculated separately for daytime and overnight periods.

124
125 **2.1.3 HbA1c**

126 • Baseline: Local and lab HbA1c values collected at the 26-week visit in the preceding 6-month
127 RCT will serve as baseline.
128 • Follow-up: Local and lab HbA1c values collected at the 13-week visit will serve as follow-up
129 values.
130 • For continuous outcome models, both local and lab values will be used. For binary outcomes, lab
131 values will be used (if lab value is missing, the local value will be used instead).

133 **2.1.4 Questionnaires**

134 The questionnaires administered at the 26-week visit in the preceding 6-month RCT will serve as
135 baseline, in addition to the Technology Expectations Survey at baseline of the current study for
136 participants who had been assigned to SAP during the preceding 6-month RCT.

137 All questionnaires will be administered online and participants/parents can skip specific questionnaires
138 or items within a questionnaire. All questionnaires will be scored according to the instructions given in

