421 Consequently, there will not be an attempt to adjust for multiplicity.

422

423 **3.3. Analysis Cohorts**

424 **3.3.1 Per-Protocol Analyses**

425

- 426 • Safety outcomes will be reported for all enrolled participants.
- 427 • If more than 5% of participants have fewer than 50% data (or <1,092hr) of post-enrollment CGM
428 data, then selected CGM analyses will be replicated excluding such participants.
- 429 • Selected CGM and HbA1c analyses will be replicated including only those participants who used
the CLC system for >80% overall.

430
431
432
433

434 **3.4. Primary and other CGM Metrics Analyses**

435

436 This study primary outcome is CGM measured % time in range 70-180 mg/dL over 13 weeks.
437

438 Summary statistics (mean \pm SD or median (quartiles)) will be reported for the CGM metrics and for
439 differences from pre-enrollment.

440 The before/after values will be compared using paired t-tests. Paired differences will be examined for an
441 approximate normal distribution. If the differences are highly skewed, then a Wilcoxon signed-rank test
442 will be used instead.

443

444

445 **3.5. HbA1c Analyses**

446 Summary statistics (mean \pm SD or n(%)) will be reported for the central lab HbA1c (continuous
447 variable) at randomization and 13-weeks. If the central lab values are missing, then the local values will
448 be used instead. The before/after values will be compared using paired t-tests. Paired differences will be
449 examined for an approximate normal distribution. If the differences are highly skewed, then a Wilcoxon
450 signed-rank test will be used instead.

451 For the binary HbA1c outcomes listed above, a McNemar test will be used.

452

453

454 **3.6. Questionnaires, Insulin, Weight, and BMI Analyses**

455 For questionnaires, insulin, weight, and BMI metrics comparisons between before/after will be made
456 using similar methods as described above in Section 3.4 for the primary analysis.

457

458

459 **3.7. Safety Analyses**

460 The safety metrics will be the same as those listed above in Section 2.7 and will be analyzed in a similar
461 manner except that there are no treatment groups for this objective and no formal statistical
462 comparisons.

463

464

465 **3.8. Device Issues**

466 Same as above in Section 2.8, except no randomization and no treatment groups.

467

468

469 **3.9. Protocol Adherence and Retention**

470 Same as above in Section 2.9, except no treatment groups.

471

472

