473 **3.10. Baseline Descriptive Statistics**

474 Same as above Section 2.10, except no treatment groups.

475

476

477 **3.11. Other Tabulations**

478 Same as above Section 2.11, except no treatment groups.

479

480

481 **3.12 Planned Interim Analyses**

482 The DSMB will review data as described above in Section 2.12.

483

484

485 **3.13. Subgroup Analyses**

486 No subgroup analyses will be performed for this objective.

487

488 **3.14. Multiple Comparison/Multiplicity**

489 No formal correction will be done for multiple comparisons.

490

491

492 **3.15. Additional Tabulations and Analyses**

493 Similar as described above in Section 2.15 with no stratification by treatment group.

494 **4. Objective 3**

495 To obtain additional safety data by continuing use of the Control-IQ system until it becomes
496 commercially available

497 • Design and Outcomes: Observational study of initiation and use of CLC for 3 months
498 following use of PLGS for 3 months. For all participants, use of the CLC system between the
499 end of 3-month period and the point that the system becomes commercially available in order
500 to gather additional safety data. All safety outcomes will be tabulated and certain exploratory
501 analyses will be conducted, analyzing metrics as change from baseline (using PLGS) to study
502 period (using CLC).

503 • The sample size will depend on how many subjects complete the preceding 6-month RCT,
504 consent to participate in the extension, and continue in the study after the initial 3 months of
505 the extension until the system becomes commercially available.

506

507 **4.1 Outcome Measures**

508 **4.1.1 Endpoints**

509 CGM Metrics

510 • Overall Control and Hyperglycemia

511 o CGM-measured % in range 70-180 mg/dL.

512 o CGM-measured % above 180 mg/dL

513 o CGM-measured mean glucose

514 o % >250 mg/dL

515 o % >300 mg/dL

516 o high blood glucose index

517 o % in range 70-140 mg/dL

518 • Hypoglycemia

519 o % below 70 mg/dL

520 o % below 54 mg/dL

521 o % below 60 mg/dL

522 o low blood glucose index

523 o hypoglycemia events (defined as at least 15 consecutive minutes <70 mg/dL)

524 • Glucose variability

525 o Coefficient of variation (CV)

526 o Standard deviation (SD)

527 • CGM metrics by time of day. Calculate all CGM metrics listed above (including the primary
528 outcome) for:

529 ○ All 24 hours of the day
530 ○ Daytime only (06:00AM to 11:59AM)
531 ○ Nighttime only (00:00AM to 05:59AM)

532

533 *HbA1c*

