534 • HbA1c at 26, weeks, every 13 weeks until the end, and/or at the final visit
535 • HbA1c <7.0% at 26weeks, every 13 weeks until the end, and/or at the final visit
536 • HbA1c <7.5% at 26weeks, every 13 weeks until the end, and/or at the final visit

537

538 *Questionnaires:*

539 • System Usability Scale (SUS) at final visit – barriers, benefits, and total score
540 • Control-IQ Patient-Reported Outcomes Questionnaire at final visit

541

542 *Other*

543 • Insulin at 26weeks, every 13 weeks until the end, and/or at the final visit
544 ○ Total daily insulin (units/kg)
545 ○ Basal: bolus insulin ratio

546

547

548 **4.1.2 Calculation of CGM Metrics:**

549 • Baseline: CGM data between enrollment or randomization and 13-week visit will be used to
550 calculate baseline metrics. At least 168 hours of CGM data will be required for the calculation.
551 Baseline CGM metrics will be treated as missing for any participants who have fewer than 168
552 hours of data.

553 • Follow-up: CGM metrics will be calculated by pooling all data starting after 13-week visit date.
554 At least 168 hours of CGM data will be required for the calculation.

555 • All CGM metrics at baseline and during follow-up will be calculated giving equal weight to each
556 sensor reading for each participant.

557 • Daytime and nighttime
558 ○ CGM metrics above will also be calculated for daytime period (06:00AM to 11:59PM)
559 and overnight period (00:00AM to 05:59AM) separately.

560 ○ Minimum 126 hours of CGM data will be required to calculate daytime metrics and
561 minimum 42 hours of CGM data will be required to calculate overnight metrics.

562 ○ If <168 hours of CGM data available for combined day and night, then CGM metrics will
563 not be calculated separately for daytime and overnight periods.

564

565 **4.1.3 HbA1c**

566 • Baseline: Lab HbA1c values collected at the 13-week visit will serve as baseline. If the lab is
567 missing, then the local value will be used instead.

568 • Follow-up: Local HbA1c values collected at the 26-, week, every 13 weeks until the end, and/or
569 at the final visit will serve as follow-up values.

570

571 **4.1.4 Analysis Windows**

572 Analysis windows apply to HbA1c outcomes measured at baseline (13-week visit) and to HbA1c,
573 insulin, and questionnaires outcomes at the follow-up 26-week, every 13 weeks until the end, and/or at
576 the final visits.

577 This does not apply to the CGM metrics which are calculated as described above.

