579 Data from follow-up visits occurring in the following windows will be included in analysis:

Visit (Target Date)	Metrics ^a	From Day ^b	Thru Day ^b
13-week visit (91 days) - Baseline	H	78	105
26-week visit of (182 days)– Follow-up	H,I	169	196
every 13 weeks until the end (273, 364, and so on days)– Follow-up	H,I	260, 351, and so on	287, 378, and so on

581 a – H = HbA1c, I = Insulin metrics.

582 b – Days from randomization/enrollment, inclusive.

583

584 **4.2 General Approach**

585 Same as described above in Section 3.2.

587

588 **4.3. Analysis Cohorts**

590 Same as described above in Section 3.3.

591

592 **4.4. Primary and other CGM Metrics Analyses**

593 Analyses will be similar to those described above in Section 3.4 except that p-values will be calculated
594 only for before/after PLGS/CLC comparisons.

598 **4.5. HbA1c Analyses**

599 This analysis will be similar to that described above in Section 3.5 except that p-values will be
600 calculated only for before/after PLGS/CLC comparisons and the “after” HbA1c value will be the local
601 value at the final visit.

602

603

604 **4.6. Questionnaires and Insulin Analyses**

605 Same as above in Section 3.6.

606

607

608 **4.7. Safety Analyses**

609 Same as above Section in 3.7.

610

611

612 **4.8. Device Issues**

613 Same as above in Section 3.8.

614

615

616 **4.9. Protocol Adherence and Retention**

617 Same as above in Section 3.8.

618

619

620 **4.10. Baseline Descriptive Statistics**

621 Baseline demographic and clinical characteristics of the cohort of all 13-week participants will be
622 summarized in a table using summary statistics appropriate to the distribution of each variable.
623 Descriptive statistics will be displayed for the PLGS/CLC cohort and overall.

624

625 Will include:

- 626 • Age at 13-week
- 627 • Gender
- 628 • Race/ethnicity
- 629 • Diabetes duration at 13-week
- 630 • HbA1c at 13-week

631

632

633 **4.11. Other Tabulations**

634
635 Individual listings for each 13-week participant will include the following:

636 • Age, gender, race/ethnicity, duration, and HbA1c at 13-week
637 • New medications

638
639 The following tabulations and analyses will be performed:

640 • Sensor performance metrics (difference, absolute relative difference, and International
641 Organization for Standardization criteria)
642 • % time CGM data available to the system

643

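### Objective 3 is meant to compare 3 months of PLGS with 3 months of CLC, but the SAP gives the CLC period no end for CGM and no fixed date for HbA1c

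*SAP*

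**What the plan says.** Protocol 8.11 gives the Objective 3 efficacy analysis as "comparing 3 months of PLGS baseline to 3 months of CLC follow up using paired t-tests". The design statement that opens SAP section 4 begins in the same way: "Design and Outcomes: Observational study of initiation and use of CLC for 3 months", after PLGS for the same length of time. SAP 4.4 refers to SAP 3.4 for its analysis, and SAP 3.4 states: "This study primary outcome is CGM measured % time in range 70-180 mg/dL over 13 weeks".

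The operational rules differ from this:

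- **CGM.** SAP 4.1.2 takes the baseline from randomization to the 13-week visit, then says: "Follow-up: CGM metrics will be calculated by pooling all data starting after 13-week visit date". No end day follows, each reading has equal weight, and SAP 4.1.4 exempts CGM from the visit windows.
- **HbA1c.** Under SAP 4.5, p-values are "calculated only for before/after PLGS/CLC comparisons and the" follow-up value is the local HbA1c at the final visit. The window table in SAP 4.1.4 has no row for that visit.
- **Timing of the final visit.** Protocol 3.8.4 continues 13-weekly visits as follows: "Until the point that the CLC system is commercially available (but not longer than 15 months" after enrollment). Protocol 3.8.5 sets the final visit by market availability or, once 15 months "has elapsed since enrollment), participants will return to the clinic within a 6-week period for a" last visit.
- **Completeness.** SAP 4.3 carries over from SAP 3.3.1 a limit of 50% of CGM data, also expressed as 1,092 hours.

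Objective 1 does have an end rule. SAP 2.1.2 stops CGM follow-up at the preceding "midnight of the earlier of day 98 from enrollment/randomization or the 13-week visit date, will" count. Objective 2 inherits that rule through SAP 3.1.

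**The concern.** Objective 3 has two parts: a before/after comparison in participants who move from PLGS to CLC, and safety follow-up of everyone until the system reaches the market. Open-ended data suit the second part. The SAP applies the same open-ended period to the first part, which is the comparison to which SAP 4.4 and 4.5 confine p-values.

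The tested CLC period would then differ from the 13-week baseline and between participants, according to when each enrolled and when the product became available. The result would not be the 3-month contrast in Protocol 8.11. A programmer would also have to choose between the 13-week outcome imported from SAP 3.4 and the unlimited pooling in SAP 4.1.2.

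For HbA1c there is a further gap. Protocol 3.8.5 lets the final-visit measurement be skipped if a 13-weekly visit fell in the preceding 2 weeks, and SAP 4.5 names no replacement.

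**Working it through.** **Inputs.** Baseline: 13 weeks = 91 days (SAP 4.1.2 and 4.1.4). Limit on follow-up: 15 months from enrollment, plus 6 weeks = 42 days (Protocol 3.8.4 and 3.8.5). Completeness limit: 1,092 hours (SAP 3.3.1, through 4.3). Assumptions: one month = 365.25/12 = 30.4375 days, the 13-week visit falls on day 91, and sensors are worn evenly over time.

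**The plan's own figure.** 0.5 × 91 × 24 = 1,092 hours, an exact match. The limit therefore equals 50% only when the window is 13 weeks.

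**Longest follow-up.** 15 × 30.4375 = 456.6 days, and 456.6 − 91 = 365.6 days on CLC. With the 6-week period, 365.6 + 42 = 407.6 days.

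**Formulas.** With L = final-visit day − 91:

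- ratio to baseline = L/91
- share of readings from the first 3 months of CLC = 91/L, at most 100%
- 1,092 hours as a share of the window = 1,092/(24 × L)

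| Final visit | L (days) | Ratio | Share from first 3 months | 1,092 h as share of window |
|---|---|---|---|---|
| Week 20 (day 140) | 49 | 0.54 | 100% | 92.9% |
| Week 26 (day 182) | 91 | 1.00 | 100% | 50% |
| Week 39 (day 273) | 182 | 2.00 | 50% | 25% |
| Week 52 (day 364) | 273 | 3.00 | 33% | 16.7% |
| 15 months | 365.6 | 4.02 | 24.9% | 12.4% |
| 15 months + 6 weeks | 407.6 | 4.48 | 22.3% | 11.2% |

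At the limit, 75 to 78% of the pooled readings come from outside the period that Protocol 8.11 specifies.

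**What this could do to the estimate.** The documents give no variance, effect size or actual follow-up lengths for Objective 3, so this is an illustration only. Suppose time in range after the first 3 months of CLC differs by d points from its value during those months. The pooled value then differs from the 3-month value by (1 − share) × d. With an assumed d of 2 points, that is 1.0 point at week 39, 1.33 at week 52, and 1.50 to 1.55 at the limit. With d = 0 there is no difference.

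**The case against.** The best defence is that the longer period was intended. The design paragraph in SAP section 4 goes on to describe CLC use until the product is on the market, and it defines the change as running from the PLGS baseline to the CLC study period without giving a length. Protocol 8.1 does the same. On that reading, SAP 4.1.2 and 4.5 agree with each other. SAP 4.4 also calls its methods only similar to those of 3.4, so the 13-week outcome may not have been meant to carry over. This is a fair account of how the text may have arisen, but unspecific wording does not override the explicit 3 months in Protocol 8.11.

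Several limiting points stand:

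- Safety is the primary outcome of Objective 3, and every before/after comparison is exploratory.
- Unequal length does not by itself bias a mean or a percentage, and the documents give no evidence of drift on CLC.
- The 26-week HbA1c is already a listed endpoint with a window of days 169 to 196, and the 4-week tabulations (SAP 4.15, through 3.15 and 2.15) describe early CLC use. Neither changes what is tested.
- The 1,092 hours stand in parentheses beside the 50% rule and trigger only a conditional repeat analysis.
- SAP 4.6 imports paired tests for insulin and questionnaires without the PLGS/CLC restriction, so the limit on p-values is clear only for CGM and HbA1c.
- The SAP was checked against protocol version 6.0, which is not available here. The comparison above is with version 6.1, dated two days after the SAP.

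**Conclusion.** The concern holds. Protocol 8.11 and SAP 4.1.2 and 4.5 specify different comparisons, and following the SAP to the letter does not produce the one in the protocol. The mismatch ranges from none, if the final visit is at week 26, to a CLC period 4.0 to 4.5 times the baseline at the protocol's limit. A final visit before week 26 gives a CLC period shorter than planned. The reading shares assume even sensor wear and a 13-week visit on day 91, and actual final-visit dates are not given. The textual conflict is certain, but its effect on the estimate is unknown and depends on whether control changes with time on CLC. No confirmatory conclusion is at risk. It should be corrected because the tested contrast is otherwise ambiguous and the correction is cheap.

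**What to change.** 1. **SAP 4.1.2.** For the PLGS-to-CLC comparison, end CGM follow-up at the midnight before the earliest of the 26-week visit, the final visit or day 189. Day 189 is 182 + 7, parallel to day 98 = 91 + 7 in SAP 2.1.2. Day 196 would instead match the 26-week window in SAP 4.1.4. Both days count from enrollment, so a 13-week visit on day 105, the last day its window allows, leaves 189 − 105 = 84 days of CLC. Summarize later CGM data descriptively.
2. **SAP 4.5.** Base the PLGS/CLC p-value on the 26-week local HbA1c, or on the final-visit value when that visit comes before week 26. Report how many participants this affects and their time on CLC.
3. **SAP 4.3.** Replace 1,092 hours with 50% of the hours in the window analysed, counted from the 13-week visit.
4. **SAP 4.7 (clarification only).** State that Objective 3 safety events and person-time run from after the 13-week visit to the final visit or contact. The cross-references from 4.7 through 3.7 to 2.7 could be read as importing Objective 1's cut-off at week 13.

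If the longer period was intended, Protocol 8.11 should be amended to say so, with the 26-week analysis as a supplement.

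**Cost.** No new procedures are needed, because Protocol 3.8.4 already schedules HbA1c and a device download at week 26. The SAP wording changes, and possibly the separate table shells. Data after week 26 leave the paired test, and participants who finish earlier contribute less than 3 months of CLC.

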805 that is accompanied by vibration followed by vibrations and/or sound if not acknowledged by the
806 user in 5 minutes. This alert remains on the screen until acknowledged by the user. The user is
807 prompted to test blood sugar and treat with carbs.

808 **4.2.4 Hyperglycemia Threshold Alert and Safety Protocol**

809 During the course of the study, participants will be permitted to change the CGM high glucose
810 threshold alert setting on their device or mobile app, but will be instructed to choose a value no
811 greater than 300 mg/dL.

812 The t:slim X2 with Control-IQ system will issue a predictive hyperglycemia alert (Control-IQ
813 High Alert) when the system has increased insulin delivery, but detects a CGM value above 200
814 mg/dL and does not predict the value will decrease in the next 30 minutes.

815 If the participant receives a Control-IQ High Alert, a message appears on the UI that is
816 accompanied by vibration followed by vibrations and/or sound if not acknowledged by the user
817 in 5 minutes. This alert remains on the screen until acknowledged by the user. The user is
818 prompted to check the site for occlusion and test blood glucose.

819 If a participant's CGM reading is >300 mg/dL for over 2 hours or ≥ 400 mg/dL at any point, the
820 participant will be instructed to take the following steps:

- 821 • Perform a blood glucose meter check.
- 822 • If the blood glucose is >300 mg/dL, check for blood ketones with the study ketone meter.
- 823 • If the ketone level is >0.6 mmol/L, take correction insulin, change insulin (pump) infusion
824 site and contact study staff.
- 825 • If a participant administers correction insulin via insulin syringe, participants will be
826 instructed to turn Control-IQ off for approximately four hours.

827 **Chapter 5: Testing Procedures and Questionnaires**

828 **5.1 Laboratory Testing**

829 1. HbA1c:

- 830 • Performed locally at the 13-week visit and at subsequent study visits at 13-week intervals
831 using the DCA Vantage or similar point of care device
- 832 • A blood sample will be obtained and sent to central lab for HbA1c assessment at the 13-
833 week visit.

834 2. Urine Pregnancy:

- 835 • A urine pregnancy test will be performed locally for females of child-bearing potential at
836 the Screening visit. The test will be repeated at the 13-week visit for participants
837 continuing in the study, and will be repeated at subsequent clinic visits at 13-week

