- 370 • Baseline CGM time 70-180 mg/dL
- 371 • Age at randomization
- 372 • Sex
- 373 • Race
- 374 • Clinical site
- 375 • Body mass index at randomization
- 376 • Income, education, and/or insurance status
- 377 • Baseline scores for quality of life, hypoglycemia awareness and fear questionnaires

378
379
380
381
382 **2.14. Multiple Comparison/Multiplicity**

383 All treatment group comparisons analyses will be considered exploratory/hypothesis-generating.
384 Consequently, there will not be a formal adjustment for multiplicity.

385
386
387 **2.15. Additional Tabulations and Analyses**

388 Twenty-four hours profiles with medians and quartiles lines and 4-week interval boxplots and
389 tabulations by treatment arms for:

- 391 • % below 70 mg/dL
- 392 • % above 180 mg/dL

393 • % time in range 70-180 mg/dL

394 • mean glucose

395

396 Among women who consent to collection of the menstrual information, an analysis that compares
397 outcomes at different times during the menstrual cycle will be performed overall and by contraception
398 type for selected CGM and insulin metrics.

399

400
401

3. Objective 2

402 Among individuals who used SAP in the original RCT, to asses efficacy and to obtain additional safety
403 data by initiating use of the Control-IQ system for 3 months.
404

405 **3.1 Outcome Measures**

406 The outcome measures for this objective will be the same as those listed above in Section 2.1.
407

408 **3.2 General Approach**

409

- 410 • All p-values will be two-sided.
- 411 • Standard residual diagnostics will be performed for all analyses. If values are highly skewed,
412 then an alternate transformation, nonparametric, or M estimation methods will be used instead
413 for the primary and secondary outcomes. Previous experience suggests that no transformation,
414 nonparametric, or M estimation analyses will be necessary for % time in range 70-180 mg/dL, %
415 above 180 mg/dL, mean glucose, or HbA1c. Other outcomes like % below 70 mg/dL over 13
416 weeks are skewed; however the differences from baseline are expected to follow a normal
417 distribution and there may be no need for transformation, nonparametric, or M estimation.
- 418 • All enrolled participants with non-missing baseline and post-enrollment data will be included in
419 the primary and secondary analyses.
- 420 • All before/after comparisons analyses will be considered exploratory/hypothesis-generating.

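### The Objective 3 HbA1c test pairs a central-laboratory baseline with a local follow-up value, so any difference between the two methods is counted as change on CLC

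*SAP*

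**What the plan says.** SAP 4.1.3 defines the Objective 3 baseline: "Baseline: Lab HbA1c values collected at the 13-week visit will serve as baseline". The local measurement is a fallback; if the lab value is "missing, then the local value will be used instead". The same section takes follow-up from the local series: "Follow-up: Local HbA1c values collected at the 26-, week, every 13 weeks until the end, and/or" at the final visit. SAP 4.5 limits p-values to participants who move from PLGS to CLC, and says that for them the after "HbA1c value will be the local" "value at the final visit".

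The tests come from SAP 3.5, to which 4.5 refers. They are a paired t-test (Wilcoxon signed-rank if the differences are highly skewed) and, for the cut-point outcomes, "For the binary HbA1c outcomes listed above, a McNemar test will be used". In Objective 3 those outcomes are HbA1c below 7.0% and below 7.5% (SAP 4.1.1).

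On what is measured and when, Protocol 5.1 says of local HbA1c: "Performed locally at the 13-week visit and at subsequent study visits at 13-week intervals". Protocol 3.8.3 lists both a point-of-care determination and a central-laboratory sample at week 13. Protocol Table 1 and section 5.1 schedule no central sample after that visit. Protocol 3.8.5 omits the final-visit HbA1c when a 13-weekly visit took place in the two weeks before.

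**The concern.** A paired comparison removes stable differences between people, but not a change of measuring method between the two time points. Here the method changes for every participant whose lab baseline is available. The p-value rests on this within-person change alone. Participants who were already on CLC go through the same switch, but they are only summarised and do not enter the test.

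If the local method reads lower on average, the result looks like improvement on CLC. If it reads higher, a real improvement is hidden. Participants without a lab baseline are compared local to local, so one test also mixes two definitions of change.

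A same-type pairing is available and has been set aside. Objective 1 is handled differently: SAP 2.5 models the central value at both times and uses the local one only as an auxiliary variable. Objective 3 has no bridging, calibration or sensitivity analysis for the method.

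There is also a smaller gap. SAP 4.5 fixes the after value at the final visit and does not say what applies when Protocol 3.8.5 omits that measurement. The window table in SAP 4.1.4 has no final-visit row.

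**Working it through.** The plan gives no figure to reproduce: it states no power, SD or method difference for this test.

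**Inputs**
- From the documents: about 100 randomised in Objective 1 (Protocol 8.2), allocated 1:1, so at most about 100/2 = 50 start on PLGS; two-sided p-values (SAP 3.2, applied by 4.2).
- Assumed: significance level 0.05; n = 50 (no losses) or 40; SD of the paired difference 0.4 to 0.5 HbA1c points; B = 0.05, 0.1 or 0.2 points in absolute size; no true change.

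**Size of the shift.** Let B be the mean of local minus central and m the share of participants on the local fallback. The expected change is the true change plus (1 − m)B. For B = 0.1, m = 5% gives 0.95 × 0.1 = 0.095 and m = 20% gives 0.80 × 0.1 = 0.08. Dilution is therefore slight.

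**Chance of p < 0.05 with no true change (m = 0).** This is the noncentral t distribution with n − 1 degrees of freedom and noncentrality B√n/SD. For example, n = 50, B = 0.1 and SD = 0.5 give 0.1 × 7.071/0.5 = 1.41 and a rejection probability of 0.284. A simulation of 100,000 trials gave 0.283.

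| n | SD | B = 0.05 | B = 0.1 | B = 0.2 | Observed mean change giving p = 0.05 |
|---|---|---|---|---|---|
| 50 | 0.4 | 0.139 | 0.410 | 0.934 | 0.114 |
| 50 | 0.5 | 0.107 | 0.284 | 0.792 | 0.142 |
| 40 | 0.4 | 0.120 | 0.338 | 0.869 | 0.128 |
| 40 | 0.5 | 0.095 | 0.235 | 0.694 | 0.160 |

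Over a wider SD range of 0.3 to 0.6 with n = 50, the probability runs from 0.637 down to 0.211 for B = 0.1, and from 0.996 down to 0.637 for B = 0.2.

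**Hiding a real effect.** Take a true fall of 0.2 with n = 50 and SD 0.5. Power is 0.79 when B = 0, 0.28 when the local method reads 0.1 higher, and 0.05 when it reads 0.2 higher, because the bias then cancels the effect.

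**Cut-points.** If HbA1c is normal between people with SD s, the largest shift in the share below a threshold is 2Φ(B/(2s)) − 1. With s between 0.7 and 0.9 this is 2.2–2.8 percentage points for B = 0.05, 4.4–5.7 for B = 0.1 and 8.8–11.4 for B = 0.2. These are maxima, reached only when the threshold lies midway between the two shifted means.

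**After the change.** With local values at both times a constant B cancels, the expected shift is 0, and the rejection rate returns to 0.05 (simulation 0.050).

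**The case against.** The strongest reply is that no bias has been shown. The documents do not say that B differs from zero, and the result depends heavily on it: with n = 50 and SD 0.4 to 0.5, B = 0.02 gives only about 6% rejections. That stands, and it is why the point is put as exposure to bias.

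The stakes are also limited. Safety is the primary outcome of Objective 3, and SAP 3.2 says "All before/after comparisons analyses will be considered exploratory/hypothesis-generating". This lowers the consequence. It does not justify changing the method between before and after, since exploratory status answers multiplicity and a p-value will still be reported.

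Participants already on CLC make the same switch, and their summaries could reveal an unexpected shift. That helps a careful reader but does not correct the test.

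Local is not a single method either. Table 1 allows a DCA Vantage, a comparable point-of-care device or a local laboratory. Local-to-local pairing therefore removes B fully only where a site used the same method at both visits. This condition is real and should be stated. Any variation among local devices is already present in the follow-up values, and the planned pairing adds a central-to-local switch on top.

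For the cut-points, the shift for B of 0.05 to 0.1 amounts to about 1 to 3 people in 50 (0.022 × 50 = 1.1; 0.057 × 50 = 2.9), and no McNemar error rate was calculated. That part carries less weight.

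The skipped final visit is a wording gap only, because a local value from the previous two weeks exists by construction. Finally, Protocol 8.11 describes three months of CLC follow-up whereas SAP 4.5 uses the final visit. That difference in timing is separate, and the change of method proposed here does not settle it.

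**Conclusion.** The concern holds and should be fixed. As written, SAP 4.1.3 and 4.5 carry (1 − m)B straight into an uncontrolled paired test, although local HbA1c is scheduled at both ends. If B is about 0.1 points, the nominal 5% error rate becomes roughly 24–41% for 40 to 50 participants and a paired SD of 0.4 to 0.5. At 0.05 points it is about 10–14%, and at 0.2 points 69–93%. These figures assume a 5% level, no true change and no use of the fallback. B, the SD and the number in the test are assumptions, not values from the documents. The direction of any bias is unknown. The effect is confined to an exploratory Objective 3 result and does not touch Objective 1 or the safety outcomes.

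**What to change.** - **SAP 4.1.3:** make the local week-13 HbA1c the baseline for the PLGS-to-CLC comparison, paired with local follow-up for the continuous change and for the 7.0% and 7.5% outcomes. Report how many participants lack a local baseline. The central week-13 value can stay in the descriptive tables.
- **SAP 4.5:** define the after value as the local one at the final visit or, where Protocol 3.8.5 omitted it, the local one from the 13-weekly visit in the preceding two weeks.
- **Reporting:** give the mean local-minus-central difference at week 13, where both are collected, so that B is visible. State whether each site used the same local method at both visits.
- **Minor, SAP 3.5 (Objective 2):** form each paired change from two values of the same kind, lab with lab and otherwise local with local, since the fallback can mix them there too.

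No change is needed to the Objective 1 model in SAP 2.1.3 and 2.5. The cost is SAP wording: the scheduled local measurements already supply the values, and no visit or sample is added.
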